5 COHORT DEFINITION

All data from enrolled participants will be analyzed according to the initial randomization assignment regardless of how many vaccinations they received. In the rare instance that a participant receives the wrong treatment at a specific vaccination time, the participant's safety data may also be excluded from the randomized group and examined separately. Analyses are modified intent-to-treat in that individuals who are randomized but not enrolled do not contribute data and hence are excluded. Because of blinding and the brief length of time between randomization and enrollment—typically no more than 4 working days—very few such individuals are expected.

6 POTENTIAL CONFOUNDERS

Characterization of the safety of the vaccine is susceptible to confounding by adverse events not related to the vaccine that by chance occur more often in one arm of the trial than another. Therefore analyses involving adverse events will incorporate the reported relationship to product as assessed by HVTN staff.

7 RANDOMIZATION

The randomization sequence will be obtained by computer-generated random numbers and provided to each HVTN CRS through FSTRF. The randomization will be done in blocks to ensure balance across arms. At each institution, the pharmacist with primary responsibility for dispensing study products is charged with maintaining security of the treatment assignments (except in emergency situations as specified in the HVTN Manual of Operations (MOP)).

8 BLINDING

Participants and site staff (except for site pharmacists) will be blinded as to participant treatment arm assignments (eg, vaccine or control). Study product assignments are accessible to those HVTN CRS pharmacists, DAIDS protocol pharmacists and contract monitors, and SDMC staff

who are required to know this information in order to ensure proper trial conduct. Any discussion of study product assignment between pharmacy staff and any other HVTN CRS staff is prohibited. The HVTN SMB members also are unblinded to treatment assignment in order to conduct review of trial safety.

When a participant leaves the trial prior to study completion, the participant will be told he or she must wait until all participants are unblinded to learn his or her treatment assignment.

Emergency unblinding decisions will be made by the site investigator. If time permits, the HVTN 122 Protocol Safety Review Team (PSRT) should be consulted before emergency unblinding occurs.

9 SAMPLE SIZE

The goal of the safety evaluation for this study is to identify safety concerns associated with product administration. The ability of the study to detect SAEs can be expressed by the true event rate above which at least 1 SAE would likely be observed and the true event rate below which no events would likely be observed. Specifically, for each vaccine arm of the study ($n = 15, 25$), there is a 90% chance of observing at least 1 event if the true rate of such an event is 14.3% or 8.9% or more, respectively; and there is a 90% chance of observing no events if the true rate is 0.4% or 0.7% less, respectively. For vaccine arms combined ($n = 40$), there is a 90% chance of observing at least 1 event if the true rate of such an event is 5.6% or more; and there is a 90% chance of observing no events if the true rate is 0.26% or less. As a reference, in previous AVEG HIV vaccine trials, 3.5% of control participants experienced an SAE; in HVTN vaccine trials from December 2000 through April 2014, about 4% of participants who received placebos experienced an SAE.

Probabilities of observing 0 and 2 or more events among 15, 25, or 40 vaccine recipients are presented in Table 1 (same as Table 6-1 in the Protocol) below for a range of possible true AE rates. These calculations provide a complete picture of the sensitivity of this study design to identify potential safety problems with the vaccine. For example, we see that if the true rate of AEs is 1%, there is an 86%, 78%, or 67% chance that no events will be observed in the vaccine arm of 15, 25, or 40 participants, respectively.

Table 1: Probability of observing 0 events, 1 or more events, and 2 or more events, among $n=15$, 25 or 40 vaccine recipients, for different true event rates

True event rate (%)	Pr(0/15)	Pr(2+/15)	Pr(0/25)	Pr(2+/25)	Pr(0/40)	Pr(2+/40)
1	0.860	0.010	0.778	0.026	0.669	0.061
3.5	0.586	0.095	0.410	0.218	0.240	0.411
5	0.463	0.171	0.277	0.358	0.129	0.601
10	0.206	0.451	0.072	0.729	0.015	0.920
20	0.035	0.833	0.004	0.973	<0.001	0.999
30	0.005	0.965	<0.001	0.998	<0.001	>0.999
40	<0.001	0.995	<0.001	>0.999	<0.001	<0.999

An alternative way of describing the statistical properties of the study design is in terms of the 95% confidence interval (CI) for the true rate of an AE based on the observed data. Table 2 (same as Table 6-2 in the Protocol) shows the 2-sided 95% CIs for the probability of an event based on a particular observed rate. Calculations are done using the score test method [36]. If none of the 15, 25 or 40 vaccine recipients experience a safety event, the 95% 2-sided upper confidence bound for the true rate of such events is 21.8%, 13.7% or 8.81%, respectively.

Table 2: Two-sided 95% confidence intervals based on observing a particular rate of safety endpoints for arms of size n_1 and n_2

Observed event rate	CI (%)
0/15	(0.00, 21.8)
1/15	(0.17, 31.9)
2/15	(1.66, 40.5)
0/25	(0.00, 13.7)
1/25	(0.10, 20.4)
2/25	(0.98, 26.0)
0/40	(0.00, 8.81)
1/40	(0.06, 13.2)
2/40	(0.61, 16.9)

10 STATISTICAL ANALYSIS

All data from enrolled participants will be analyzed according to the initial randomization assignment regardless of how many vaccinations they received.

Analyses are modified intent-to-treat in that individuals who are randomized but not enrolled do not contribute data and hence are excluded. Because of blinding and the brief length of time between randomization and enrollment—typically no more than 4 working days—very few such individuals are expected.

Analyses for primary endpoints will be performed using SAS and R. All other descriptive and inferential statistical analyses will be performed using SAS, StatXact, or R statistical software.

No formal multiple comparison adjustments will be employed for multiple safety endpoints, multiple primary immunogenicity endpoints, or secondary endpoints. However, multiplicity adjustments will be made for certain immunogenicity assays, as discussed below, when the assay endpoint is viewed as a collection of hypotheses (eg, testing multiple peptide pools to determine a positive response).

10.1 Analysis variables

The analysis variables consist of baseline participant characteristics, safety, and immunogenicity for primary- and secondary-objective analyses.

10.2 Baseline comparability

Treatment arms will be compared for baseline participant characteristics using descriptive statistics.

10.3 Safety/tolerability analysis

Since enrollment is concurrent with receiving the first vaccination, all participants will have received at least 1 vaccination and therefore will provide some safety data.

10.3.1 Reactogenicity

The number and percentage of participants experiencing each type of reactogenicity sign or symptom will be tabulated by severity and treatment group and the percentages displayed graphically by group. For a given sign or symptom, each participant's reactogenicity will be counted once under the maximum severity for all injection visits. In addition, to the individual types of events, the maximum severity of local pain or tenderness, induration or erythema, and of

systemic symptoms will be calculated. For the final study analysis, Kruskal-Wallis tests will be used to test for differences in severity between groups.

10.3.2 AEs and SAEs

AEs will be summarized using MedDRA System Organ Class and preferred terms. Tables will show by treatment group the number and percentage of participants experiencing an AE within a System Organ Class or within preferred term category by severity or by relationship to study product. For the calculations in these tables, a participant with multiple AEs within a category will be counted once under the maximum severity or the strongest recorded causal relationship to study product. Formal statistical testing comparing groups is not planned since interpretation of differences must rely heavily upon clinical judgment.

A listing of SAEs reported to the DAIDS Regulatory Support Center (RSC) Safety Office will provide details of the events including severity, relationship to study product, time between onset and last vaccination, and number of vaccinations received.

10.3.3 Local laboratory values

Box plots of local laboratory values will be generated for baseline values and for values measured during the course of the study by treatment group and visit. Each box plot will show the first quartile, the median, and the third quartile. Outliers (values outside the box plot) will also be plotted. If appropriate, horizontal lines representing boundaries for abnormal values will be plotted.

For each local laboratory measure, summary statistics will be presented by treatment arm and timepoint, as well as changes from baseline for postenrollment values. In addition, the number (percentage) of participants with local laboratory values recorded as meeting Grade 1 AE criteria or above as specified in the Division of AIDS Table for Grading the Severity of Adult and Pediatric Adverse Events (section 9.8 of the Protocol) will be tabulated by treatment arm for each postvaccination timepoint. Reportable clinical laboratory abnormalities without an associated clinical diagnosis will also be included in the tabulation of AEs described above.

10.3.4 Reasons for vaccination discontinuation and early study termination

The number and percentage of participants who discontinue vaccination and who terminate the study early will be tabulated by reason and treatment group.

10.4 Analyses prior to end of scheduled follow-up visits

Any analyses conducted prior to the end of the scheduled follow-up visits should not compromise the integrity of the trial in terms of participant retention or safety or immunogenicity endpoint assessments. In particular, early unblinded analyses by treatment assignment require careful consideration and should be made available on a need to know basis only.

10.4.1 Safety

During the course of the trial, unblinded analyses of safety data will be prepared approximately every 4 months for review by the SMB. Ad hoc safety reports may also be prepared for SMB review at the request of the HVTN 122 PSRT. The HVTN leadership must approve any other requests for unblinded safety data prior to the end of the scheduled follow-up visits.

10.4.2 Immunogenicity

An unblinded statistical analysis by treatment assignment of a primary immunogenicity endpoint may be performed when all participants have completed the corresponding primary immunogenicity visit and data are available for analysis from at least 80% of these participants.

Similarly, an unblinded statistical analysis by treatment assignment of a secondary or exploratory immunogenicity endpoint may be performed when all participants have completed the corresponding immunogenicity visit and data are available for analysis from at least 80% of these participants. However, such analyses for a secondary or exploratory immunogenicity endpoint will only take place after at least 1 of the primary immunogenicity endpoints of the same class (humoral or cell-mediated) or, if no primary endpoint of the same class, at least 1 of the primary immunogenicity endpoints reaches the aforementioned threshold. The Laboratory Program will review the analysis report prior to distribution to the protocol chairs, DAIDS, vaccine developer, and other key HVTN members and investigators. Distribution of reports will be limited to those with a need to know for the purpose of informing future trial-related decisions. The HVTN leadership must approve any other requests for HVTN immunogenicity analyses prior to the end of the scheduled follow-up visits.

10.5 Immunogenicity analysis

10.5.1 General approach

For the statistical analysis of immunogenicity endpoints, data from enrolled participants will be used according to the initial randomization assignment regardless of how many injections they received. Additional analyses may be performed, limited to participants who received all scheduled injections per protocol. Assay results that are unreliable, from specimens collected outside of the visit window, or from HIV-infected participants postinfection are excluded. Since the exact date of HIV infection is unknown, any assay data from blood draws 4 weeks prior to an infected participant's last seronegative sample and thereafter may be excluded. If an HIV-infected participant does not have a seronegative sample postenrollment, then all data from that participant may be excluded from the analysis.

Discrete categorical assay endpoints (eg, response rates) will be analyzed by tabulating the frequency of positive response for each assay by antigen and treatment arm at each timepoint for which an assessment is performed. Crude response rates will be presented with their corresponding 95% confidence interval estimates calculated using the score test method [1]. Because of the small numbers of control participants, no adjustment will be made to the vaccine arm estimates for the false positive rates in the control arms. Barnard or Fisher's exact tests, as specified in the SAP, will be used to compare the response rates of the 2 vaccine arms, with a significant difference declared if the 2-sided p-value is ≤ 0.05 . In general Barnard's is preferred since under most circumstances it is more powerful than Fisher's [2].

For quantitative assay data (eg, IgG binding Ab response from the multiplex assay or CD4⁺/CD8⁺ T cell response from the ICS assay), graphical and tabular summaries of the distributions by antigen, treatment arm, and timepoint will be made. For all primary and secondary immunogenicity endpoints, box plots and plots of estimated reverse cumulative distribution curves will be used for graphical display of all of the study arms. Typically the results will be shown for each vaccine arm and for the control arm separately.

The difference between arms at a specific timepoint may be tested with a nonparametric Wilcoxon rank sum test if the data are not normally distributed and with a 2-sample t-test if the data appear to be normally distributed. An appropriate data transformation (eg, log₁₀ transformation) may be applied to better satisfy assumptions of symmetry and homoscedasticity (constant variance).

10.5.2 Multivariate display of immunogenicity endpoints

Data visualization techniques may be used to explore the relationship among immunogenicity readouts. The set of readouts may be based on 1 of the primary endpoints (e.g., ICS), on the set of primary endpoints, or on immunogenicity endpoints that also include secondary or exploratory

endpoints. To understand the relationship between pairs of readouts, scatter plots may be used when the number of readouts is small or for a larger number of readouts, a heat map showing the degree of correlation between any 2 pairs. Principal component analysis (PCA) and associated “biplots” of the scores and loadings are particularly useful to understand associations between readouts, especially when readouts are correlated [3]. PCA is a method to reduce the dimensionality of the number of readouts to a smaller set of values (principal components) that are normalized linear combinations of the readouts in such a way that the first principal component accounts for the most variability in the data and subsequent components, while maximizing variability, are uncorrelated with each other. A ‘biplot’ displays the first and second principal component scores and principal component loadings. The x-axis is the value from the first principal component and the y-axis is the second principal component, where each axis label includes the percentage of variation in the total set of readouts captured by the principal component. The top axis is the first principal component loadings and the right axis is the second principal component loadings. An arrow is drawn for each immunogenicity readout (eg, Env-specific CD4+ T cell polyfunctionality score, Env-specific CD8+ T cell total magnitude) from the origin to the point defined by its first 2 principal component loadings. The length of the arrow represents the amount of total variation of the set of readouts captured by the given readout. The direction of an arrow conveys the extent to which the variation of a readout is in the direction of the first or second principal component. The angle between 2 arrows conveys information about the correlation of the 2 readouts, with a 0 degree angle denoting perfect correlation and a 90 degree angle denoting no correlation. Each arrow on the biplot is labeled by the immunogenicity readout it represents. A biplot is annotated with key meta-information such as the treatment arm (most common application) or a demographic category. Depending on the application, K-means clustering and hierarchical clustering may also be applied for multivariate graphical display of immunogenicity readouts.

10.5.3 Analysis of CD4+ and CD8+ T-cell response as measured by the ICS assay

The frequency and magnitude of CD4+ and CD8+ T-cells secreting IFN- γ and/or IL-2 as measured by the 17-color ICS assay will be evaluated and compared as described under the general approach in Section 10.5.1. For each T-cell subset, the Fisher’s exact test-based positivity criteria will be used to determine the positivity call for responses to each peptide pool. The Mixture Models for Single-cell Assays (MIMOSA) statistical framework [4] for positivity may also be used as supporting analyses. If requested, the magnitude of marginal response may be analyzed as described for quantitative data in the general approach section.

For each T-cell subset, graphs will be used to display the background-subtracted magnitudes for each participant by protein, treatment arm, and timepoint. Given that multiple cytokines are measured in this study, the polyfunctionality of ICS responses may also be analyzed as an exploratory endpoint when there are a sufficient number of participants with a positive CD4+ or CD8+ IFN- γ and/or IL-2 response. To this end, besides descriptive plots of the magnitude of polyfunctional responses, the Combinatorial Polyfunctionality analysis of Antigen-Specific T-cell Subsets (COMPASS) statistical framework [5] may also be used to perform joint modelling of multiple T-cell subsets of different cytokine combinations. For example, the functionality score (FS) and the polyfunctionality score (PFS) may be used to summarize the multi-parameter ICS responses.

For data available at visit 9 (2 weeks post the third vaccination), positive response rates to Any Env will be compared between Groups 1 and 2 using the Barnard’s exact test, where a positive response to Any Env is defined as those who are positive to at least one of the tested Env peptide pools. If there are more than 5 positive responders in both treatment groups, response magnitudes among positive responder will also be compared between Groups 1 and 2 using the Wilcoxon

rank sum test, where the response magnitude is defined as the summation across the Env PTE peptide pools. Statistical tests with a p-value ≤ 0.05 will be considered statistically significant.

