#### 6.4.4.4 Secondary analysis of CD4+ and CD8+ T-cell response as measured by the ICS assay

The analysis of CD4+ and CD8+ T-cell response rates as measured by the ICS assay will be evaluated and compared as described under the general approach. For each T-cell subset, the positivity call for each peptide pool will include a multiple comparison adjustment for the number of peptide pools used in the assay. In general, the Mixture Models for Single-cell Assays (MIMOSA) statistical framework [39] and/or the Fisher's exact test-based positivity criteria will be used. Details of the positivity criteria will be discussed in the SAP. The magnitude of marginal response will be analyzed as described for quantitative data in the general approach section. For each T-cell subset, graphs will be used to display the background-subtracted magnitudes for each participant by protein, treatment arm, and timepoint. When 3 or more cytokines are being measured by the ICS assay, the polyfunctionality of ICS responses may also be analyzed as an exploratory endpoint. Besides descriptive plots of the magnitude of polyfunctional responses, the Combinatorial Polyfunctionality analysis of Antigen-Specific T-cell Subsets () statistical framework [40] may also be used to perform joint modelling of multiple T-cell subsets of different cytokine combinations. For example, the functionality score (FS) and the polyfunctionality score (PFS) may be used to summarize the multi-parameter ICS responses.

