12.1.1 List of Tables

- Response rate table by lab, T-cell subset, peptide pool, visit, day, and group/treatment arm for cells expressing either IL-2 and/or IFN- γ using Fisher's exact test criteria.
- Listing of positive responders for cells expressing either IL-2 and/or IFN- γ .
- Summary statistics (i.e., min, mean, median, max) among responders for T-cell subset, peptide pool, visit, and group/treatment arm

- Summary statistics (i.e., min, mean, median, max) among all participants (positive and negative responders) for T-cell subset, peptide pool, visit, and group/treatment arm.
- Response rate and/or response magnitude comparison of treatment arms.

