12.3.1 List of Tables

- Response rate table by lab, virus tier, virus, visit, and group/treatment arm.
- Listing of positive responders based on the criteria used for the response rate table(s).
- Summary statistics (i.e., min, geometric mean, median, max) of ID50 titers among responders by lab, virus tier, virus, visit, and group/treatment arm
- Summary statistics (i.e., min, geometric mean, median, max) of ID50 titers among all participants (positive and negative responders) by lab, virus tier, virus, visit, and group/treatment arm
- Comparisons of response rates between Group 1 vs. Group 3, Group 2 vs. Group 3, and Group 1 vs. Group 2 for each of the non-global panel viruses
- Comparisons of ID50 titers between Group 1 vs. Group 2 for each of the non-global panel viruses among responders.
- Comparisons of ID50 titers between Group 1 vs. Group 2 for each of the non-global panel viruses among all participants, with the titer of non-responders censored at 5.
- Comparison of AUC-MB between Group 1 vs. Group 2.

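### The only committed between-dose test of ICS T-cell magnitude is limited to responders and gated on their number; an ungated all-participant test should be added

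*SAP*

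**What the plan says.** Secondary objective 3 (Protocol 5.2, SAP 4.2) has an ICS endpoint with two parts at 2 weeks after the third vaccination: response rates and levels of CD4+ and CD8+ T cells.

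SAP 10.5.3 gives the specific visit 9 plan. Response rates to Any Env are compared between Groups 1 and 2 by Barnard's test, with no gate; "a positive response to Any Env is defined as those who are positive to at least one of the tested Env peptide pools". Magnitude comes second and is conditional: "If there are more than 5 positive responders in both treatment groups, response magnitudes among positive responder will also be compared". The test is a Wilcoxon "rank sum test, where the response magnitude is defined as the summation across the Env PTE peptide pools".

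Other text bears on who is included:

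- SAP 10.5.3 opens by referring both frequency and magnitude to the general approach in 10.5.1. That section uses enrolled participants as randomized, and its between-arm magnitude test has no responder limit, but the test is optional (may).
- Protocol 6.4.4.4 says: "The magnitude of marginal response will be analyzed as described for quantitative data in the general approach section". SAP 10.5.3 makes the marginal analysis available on request.
- SAP 12.1.1 lists ICS magnitude summaries for responders and, separately, for everyone. Its last item, a comparison of arms on rate and/or magnitude, names no population.
- SAP 12.3.1, for neutralizing antibody, lists a responder-only comparison and also "Comparisons of ID50 titers between Group 1 vs. Group 2 for each of the non-global panel viruses among all participants", with non-responders set to a floor value and no gate.

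**The concern.** Whether a participant is a responder is an outcome, and dose may change it. If 300 mcg lifts weak participants just over the positivity line, they enter the Group 1 responder set with low values, while their counterparts in Group 2 are left out. The two responder sets are then no longer the groups that randomization made comparable. In this situation the difference in level is understated.

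The gate adds a second condition. Group 2 is the smaller arm, so it decides whether the level comparison is run. If it responds poorly, no committed test of levels remains, although levels are half of the stated endpoint.

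**Working it through.** **Inputs from the documents.** Enrolled 25 (Group 1) and 15 (Group 2), with 10% missing immunogenicity data (Protocol 6.1 and 6.1.2): 0.9 × 25 = 22.5 and 0.9 × 15 = 13.5, used there as 22 and 13. More than 5 means at least 6 responders per arm. Significance level (SAP 10.5.3): "Statistical tests with a p-value ≤ 0.05 will be considered statistically significant". Two-sided testing is taken from SAP 10.5.1, where it is stated for response rates.

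**Assumed.** The documents give no expected ICS response rate and no standard deviation. Rates of 30% to 70% are used as a range.

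**The plan's own figures.** The documents state no chance of meeting the gate and no power for the magnitude test. Table 6-3 at the same sample sizes can be reproduced with the Wilson score interval, [p + z²/2n ± z√(p(1−p)/n + z²/4n²)] / (1 + z²/n). For 7/13: centre (0.5385 + 0.1478)/1.2955 = 0.530, half-width 1.96 × 0.1575/1.2955 = 0.238, giving 29.1% to 76.8% as printed. All 21 rows agree within 0.1 point.

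**Chance that the gate is met.** P = P(Bin(22, p₁) ≥ 6) × P(Bin(13, p₂) ≥ 6).

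| Common rate | Group 2 has ≥ 6 of 13 | Group 1 has ≥ 6 of 22 | Gate met | Gate met, no missing data (15, 25) |
|---|---|---|---|---|
| 30% | 0.165 | 0.687 | 0.11 | 0.23 |
| 40% | 0.426 | 0.928 | 0.40 | 0.58 |
| 50% | 0.709 | 0.992 | 0.70 | 0.85 |
| 60% | 0.902 | 1.000 | 0.90 | 0.97 |
| 70% | 0.982 | 1.000 | 0.98 | 0.996 |

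Group 2 must show 6/13 = 46%. The gate is met half the time at a common rate of about 43% (38% with no missing data). A higher Group 1 rate changes little: 0.16 at 50% versus 30%, and 0.71 at 70% versus 50%.

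**Effect of selecting responders.** Assumed model: log magnitude is normal with SD 1, Group 1 is shifted up by 0.8 SD, and a participant responds if above a threshold fixed by the Group 2 rate. The all-participant version ties every non-responder at the threshold. Entries are the percentage of simulated trials significant at 0.05, two-sided.

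| Group 2 rate | Gated responder-only Wilcoxon | All-participant Wilcoxon | Barnard on rates | Barnard or gated Wilcoxon |
|---|---|---|---|---|
| 30% | 2 | 48 | 39 | 41 |
| 40% | 7 | 50 | 40 | 46 |
| 50% | 14 | 54 | 41 | 52 |
| 60% | 21 | 55 | 43 | 57 |
| 70% | 29 | 57 | 37 | 58 |

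The two Wilcoxon columns come from 6,000 trials per row and the last two from a separate run of 3,000. Repeat runs move the entries by about two points.

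Among responders, the mean difference shrinks from 0.8 SD to about 0.3 to 0.5 SD. At a 70% rate the gate is met 98% of the time, yet the responder-only test has about half the power of the all-participant test, so the gate is not the whole cause. With no dose effect, neither Wilcoxon test rejects materially more than 5% of the time.

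**The case against.** The strongest reply is that the plan is a two-part analysis: response rate in everyone, then magnitude given response. That is a recognised approach, and its first part is ungated and as randomized. A reader might infer from the gap between 2% and 48% that the trial would miss a real dose effect. The documents do not support that. When dose moves people over the positivity line, the planned Barnard test sees it, and the chance that either planned test is significant (41% to 58%) is within about 8 points of the all-participant test throughout, and level with it from 60% upward. The comparison is not quite even, because two tests raise the null rate to about 5% to 9%. The reply stands as regards detecting any dose effect. It does not supply an unselected comparison of levels.

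A reader might also infer that the test will usually not be run. That depends on a rate the documents do not state: likely so below about 43%, not so at 60% or more.

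Nor does the SAP rule out an all-participant test or remove a mandatory one. SAP 10.5.1 permits it, the comparison item in SAP 12.1.1 could cover it, and the protocol sentence concerns marginal responses under a general approach whose test is itself optional. What remains is that no such test is committed.

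Finally, SAP 12.2.1 also limits binding-antibody magnitude comparisons to responders (with at least 5 per group), so the ICS restriction is not unique. That shows consistency with one assay; it does not make responder sets comparable.

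**Conclusion.** The point holds in limited form. The single committed ICS level comparison between doses is made in a subset defined after randomization, and only if each arm has at least 6 such participants. Under the assumed model it understates a 0.8 SD shift as about 0.3 to 0.5 SD and is significant in about 2% to 29% of trials, against about 48% to 57% for an all-participant test.

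The gate probabilities are exact for the assumed rates. The attenuation and power figures rest on the normal threshold model. If dose raised magnitude only in people who would respond at either dose, the attenuation would disappear.

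Severity is low. This is a secondary, unpowered phase 1 comparison, response rates are tested without a gate, and all-participant magnitudes are already tabulated by arm.

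**What to change.** In SAP 10.5.3 and 12.1.1 add, for each T-cell subset, a two-sided Wilcoxon rank sum test of Group 1 versus Group 2 on the summed background-subtracted Env magnitude, in all participants with visit 9 data, whether or not they responded and with no minimum number of responders. SAP 12.3.1 is the model. Label the responder-only comparison as descriptive.

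The cost is one sentence and one extra test per T-cell subset, on data already tabulated. The downside is that the all-participant test mixes response rate with magnitude, so it should be reported and read beside the Barnard test.
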